8.1.8 Clinical Laboratory Evaluations

Clinical laboratory safety testing will be collected at the time points described in the Schedule of Assessments ([Table 1](#) and [Table 2](#)) and recorded in the eCRF and source documents. Safety laboratory samples will be analyzed at a central laboratory. Local testing on these samples may be conducted, as clinically indicated.

The parameters to be assessed are presented in [Table 9](#).

Table 9 Clinical Laboratory Parameters

| Hematology | Coagulation | Clinical chemistry | Urinalysis |
|--|--|--|--|
| 
Complete blood count, including:
 
 White blood cell count (with differential) Red blood cell count Hemoglobin Hematocrit Platelet count Reticulocyte count Mean corpuscular volume Mean corpuscular hemoglobin Mean corpuscular hemoglobin concentration High sensitivity C-reactive protein (hsCRP) Fibrinogen Complement (C3 and Bb)^a | 
Activated partial thromboplastin time
 
Prothrombin time
 
International Normalized Ratio
 | 
Sodium
 
Potassium
 
Chloride
 
Bicarbonate
 
Blood urea nitrogen
 
Creatinine
 
Creatine phosphokinase
 
Alanine aminotransferase
 
Aspartate aminotransferase
 
Alkaline phosphatase
 
Bilirubin
 
Gamma glutamyl transferase
 
GLDH
 
Serum Cystatin C
 
Hepatitis B surface antigen test^b
 
Hepatitis C antibody test^b
 
Cardiac Troponin 1
 | 
pH
 
Specific gravity
 
Urine osmolality
 
Glucose
 
Ketones
 
Blood
 
Urobilinogen
 
Bilirubin
 
Microscopic examination for RBCs and WBCs
 
Quantitative analysis of protein
 |

^a Complement will not be tested at Screening.

^b Tested only at Screening

8.2 Pharmacokinetic Assessments in Japanese PK Cohort Patients

PK blood samples will be collected according to [Table 3](#). Additional PK time points may also be collected from these patients as mentioned in Section [8.3](#).

8.3 Pharmacokinetic Assessments (Overall)

Sparse sampling for all patients will be collected per [Table 4](#) and Table 5. Blood samples will be collected for analysis done by a Sponsor-approved CRO using a validated method. Samples will only be used by the Sponsor and/or a contracted vendor for research related to the development of treatments for DMD, and will be stored for a maximum of 15 years. All biological material will be stored and secured in a way that ensures that unauthorized access is prohibited, and the samples are not lost, deteriorated, or destroyed accidentally or illegally. Detailed instructions for sample collection, storage, processing, and shipping will be provided in the study-specific manual.

8.4 Immunogenicity

Immunogenicity samples will be collected to assess anti-drug and anti-dystrophin antibodies in serum, according to the Schedule of Assessment ([Table 6](#) and [Table 7](#)).

Samples will only be used by the Sponsor and/or a contracted vendor for research related to the development of treatments for DMD and will be stored for a maximum of 15 years. All biological material will be stored and secured in a way that ensures that unauthorized access is prohibited, and the samples are not lost, deteriorated, or destroyed accidentally or illegally. Detailed instructions for sample collection, storage, processing, and shipping will be provided in the study-specific manual.

8.5 Pharmacodynamic Assessments

Tissue samples collected from muscle biopsies ([Section 4.1](#)) will be evaluated for changes in dystrophin protein level, dystrophin localization, and presence of exon 51-skipped mRNA transcript following treatment with WVE-210201.

Samples will only be used by the Sponsor and/or a contracted vendor for research related to the development of treatments for DMD and will be stored for a maximum of 15 years. All biological material will be stored and secured in a way that ensures that unauthorized access is prohibited, and the samples are not lost, deteriorated, or destroyed accidentally or illegally. Detailed instructions for sample collection, storage, processing, and shipping will be provided in the study-specific manual.

8.5.1 *Dystrophin Localization*

Muscle biopsy samples will be used to assess the effect of WVE-210201 on dystrophin protein localization by immunohistochemistry/immunofluorescence.

8.5.2 *Exon 51-Skipped mRNA in Muscle Tissue*

Muscle biopsy samples will be used to evaluate the effect of WVE-210201 on the presence of exon 51-skipped mRNA by RT-PCR.

8.6 Muscle Concentration of WVE-210201

WVE-210201 concentration in muscle tissue by ELISA (if adequate tissue sample is available) may be evaluated.

8.7 Efficacy Assessments

8.7.1 *Dystrophin Quantification by Western Blot*

Levels of dystrophin may be quantified by Western blot in the muscle tissues collected at baseline and at one of three postbaseline time points, according to [Section 4.1](#).

The amount of restored dystrophin protein from muscle tissues will be evaluated using a validated Western blot method, according to a detailed validation protocol.

8.7.2 *Functional Assessments*

Functional assessments that are included in both NSAA and Timed Function Tests, will only be administered once per timepoint.

Functional assessments must be performed pre-dose on: Weeks 1, 12, 24, 36 48, 60, 72, 84 and 96 (on the dosing day or up to 24 hours prior to the indicated dosing day) in the order listed below:

See the [Table 1](#), [Table 2](#) and the Study Manual for additional information

- NSAA (will also be done at screening)
- PUL 2.0
- Timed function test 4-stair climb
- Hand-held myometry
- Pulmonary function tests (PFR, CPF, and FVC); FVC will be done at screening as well.

PedsQL ([Section 8.7.3](#)) assessments must be performed pre-dose on Weeks 1, 48, and 96 (on the dosing day or up to 24 hours prior to indicated dosing day), in the following order:

- PedsQL-NMM and GCS
- NSAA
- PUL 2.0
- Timed function test 4-stair climb

- Hand-held myometry
- Pulmonary function tests (PFR, CPF, and FVC); FVC will be done at screening as well.

8.7.2.1 *North Star Ambulatory Assessment*

The NSAA is a validated unidimensional scale, designed for measuring motor function in ambulatory boys with DMD^{45,46}. The scale is suitable for multicentric global studies and is widely used internationally as a relevant functional assessment for patients with DMD. The scale was specifically designed for ambulant children with DMD. NSAA includes 17 items, ranging from standing (item 1) to running (item 17), that are necessary to remain functionally ambulant. The scale includes items assessing abilities, such as head raise and standing on heels that can be present in the early stages of the disease and other activities such as hopping, or running that are generally never fully achieved in untreated DMD boys⁴⁷.

Each item is scored on a 3-point scale using simple criteria:

2 - Normal; achieves goal without any assistance

1 - Modified method but achieves goal independent of physical assistance from another person

0 - Unable to achieve independently

The total score is the sum of the individual item scores. The score can range from 0, if no activities can be achieved independently, to 34, if all the activities can be achieved without any assistance. The scale is generally completed in a maximum of 15 minutes.

8.7.2.2 *Timed Function Tests*

The time to climb 4 standard-sized stairs will also measure lower limb motor function in ambulatory patients. Other timed-function tests, 10-m walk/run and rise from floor will be performed by the patient only once as part of NSAA, and will not be re-administered. These tests will be recorded on both NSAA and TFT scales.

8.7.2.3 *Performance of Upper Limb (PUL 2.0) Test*

The PUL test is an assessment tool that evaluates upper limb function in ambulatory and non-ambulatory DMD patients and was developed through a collaborative international group including boys with DMD and their families. The PUL test was designed with a conceptual framework reflecting the progression of weakness and the natural history of functional decline in DMD⁴⁸.

8.7.2.4 *Hand-held Myometry*

Upper limb proximal strength will be assessed by handheld myometry^{49,50}.

8.7.2.5 Pulmonary Function Tests

Pulmonary function tests (PFR, CPF, and FVC)⁵¹ will be performed using the Microlab Spirometer.

- Peak flow rate (PFR) and cough peak flow (CPF): Muscle weakness caused by neuromuscular disorders results in reduced values for peak flow rate. This test is effort dependent. The use of CPF can minimize effort-related variation. Thus, for patients with neuromuscular weakness, CPF measured by peak flow meter is a reliable measurement of expiratory muscle strength.
- Forced vital capacity (FVC): During the FVC assessment, the patient takes a maximum breath and fills his lungs to total lung capacity (TLC) and then exhales to the maximum. The total volume of air expelled during forced exhalation after maximum inspiration is the FVC. The values are reduced in patients with neuromuscular disease. Measurements of FVC will be collected while the patient is in the sitting position. If the patient is wearing a thoracolumbar device, the measurements will be taken with the device on, and the patient in a sitting position

8.7.2.6 ActiMyo Wearable Device

ActiMyo is a wearable device that has been developed to quantify a patient's ambulation ability directly and reliably in a continuous manner in the home environment. Data collection will be performed at the time points listed in [Table 7](#) Immunogenicity Sample Collection-Open-label Period

| Week 60 | Week 72 | Week 96 (or ET) |
|----------|----------|-----------------|
| Pre-dose | Pre-dose | Pre-dose |
| X | X | X |

[Table 8](#). The device consists of two sensors: one worn on the ankle and one worn on the wrist. The two sensors must be worn on the same side and must be worn on the chosen side consistently throughout the study. The device is put on in the morning and worn throughout the day, removed at night, and placed in a docking station for charging and data upload. The device will be given to patients during the Screening Period and worn, as instructed ([Table 6](#)). The ActiMyo device will only be used during the double-blind treatment period.

The device recordings will be processed to generate measures of ambulation ability and maximal ambulation performance. These variables include the following:

- percentage of time walking
- distance walked
- median stride velocity

- 95th percentile stride velocity
- median stride length
- 95th percentile stride length
- number of falls

8.7.3 *Quality of Life*

The PedsQL is a brief, standardized, generic assessment instrument that systematically assesses pediatric patients' and parents' perceptions of HRQOL in pediatric patients with chronic health conditions. Considered a clinically important patient-rated outcome (PRO) of patient care, HRQOL characterizes the perceived effect of a disease, condition, illness, injury, or treatment intervention on various health domains (eg, physical, emotional, social). The PedsQL is a modular instrument for measuring HRQOL in children and adolescents aged 2 to 18. The PedsQL 4.0 Generic Core Scales are multidimensional pediatric patient self-report and parent proxy-report scales developed as the generic core measure to be integrated with the PedsQL Disease-Specific Modules. A disease specific module of the PedsQL (Pediatric Quality of Life Inventory), the PedsQL 3.0 Neuromuscular Module (NMM), will be administered together with the PedsQL 4.0 Generic Core Scales⁵². This assessment is development-appropriate and will be done according to the Schedule of Assessments ([Table 1](#)). Please refer to Section 8.7 for the sequence of assessments.

8.7.3.1 *Pediatric Quality of Life Inventory (Neuromuscular Module)*

The PedsQL offers a modular approach to measuring health-related quality of life (HRQOL) in healthy children and adolescents and those with acute and chronic health conditions, and is responsive to clinical change over time. PedsQL Neuromuscular Module is a specific module of the PedsQL, and is used for measuring HRQOL in patients with DMD⁵².

8.7.3.2 *Pediatric Quality of Life Inventory (Generic Core Scale)*

Given the importance of HRQOL in patient care, efforts have been directed over the last decade to developing generic PRO instruments to evaluate HRQOL during care. The PedsQL GCS (version 4.0) is a generic PRO instrument that evaluates HRQOL in patients aged 2 to 18 years^{53,54}. Pediatric self-report is measured in children and adolescents aged 5-18 years, and parent proxy-report of child HRQOL is measured for children and adolescents aged 2-18 years. The 23-item PedsQL GCS consists of four subscale scores and two summary scores. The PedsQL GCS subscales include physical functioning (PF, 8 items), emotional-functioning (EF, 5 items), social-functioning (SOF, 5 items), and school-functioning (SCF, 5 items). The total score (TS, 23 items) is a summary score of all subscale scores, and the psychosocial functioning score (PSF, 15 items) is a summary score of the EF, SOF, and SCF subscale scores. Each item is rated on a 5-point Likert scale.

8.7.4 *Milestone Events*

The occurrence of milestone events (loss of ambulation, loss of ability to self-feed and need for day time ventilation) will be derived using observations from the NSAA, PUL 2.0 and pulmonary function tests.

9 ADVERSE EVENTS

The Investigator is responsible for reporting all AEs that are observed or reported during the study, regardless of their relationship to study treatment or their clinical significance.

Adverse event information will be collected from the date of signed informed consent and up to the end of the study. All ongoing AEs at the end of the study will be followed to resolution or until the Investigator and the Sponsor agree that further follow-up is not required.

An AE is defined as any untoward medical occurrence in a patient enrolled into this study regardless of its causal relationship to study treatment. Patients and parents/legal guardians/caregivers will be instructed to contact the Investigator at any time after the patient/parent/legal guardian signs informed consent, if any symptoms develop while the patient is in the study.

If a patient is hospitalized for a pre-planned elective medical or surgical procedure, or is admitted as an in-patient for a pre-planned observation period post-study drug administration (refer to [Section 6.2.2](#)) this will not be recorded as an SAE unless associated with an untoward medical occurrence that meets the definition of a serious event as outlined in [Section 9.3.1](#) (e.g. bleeding event after surgery that prolongs hospitalization). Such hospitalization must be documented in advance in the patient's medical record and the reason should be described in detail.

A TEAE is defined as any event not present before exposure to study treatment or any event already present that worsens in either intensity or frequency after exposure to study treatment.

9.1 Eliciting and Documenting Adverse Events

All AEs reported or observed during the study, including AEs resulting from concurrent illnesses, reactions to concurrent medications, or progression of disease states, will be recorded on the AE page in the eCRF and in the site source notes. The eCRFs used to document AEs are designed to help ensure this information is collected in a standard way. Information to be collected includes the as-reported event term, date and time of onset, date and time of resolution, Investigator-specified assessment of severity and relationship to study treatment, action taken with respect to study treatment, seriousness, any required treatment or evaluations, and outcome. All AEs will be followed to adequate resolution. The sites will be provided completion guidelines for the eCRF, which will further guide them on how to record the data, including AEs. The Medical Dictionary for Regulatory Activities (MedDRA) will be used to code all AEs.

Any medical condition that is present at the time that the patient/parent/legal guardian signs informed consent but does not worsen should not be reported as an AE. However, if it worsens at

any time during the study, it must be recorded as an AE. This includes any spontaneously reported worsening of depression, i.e., not based on the study rating scales.

In addition to observations of the patient, AEs identified from any study data (e.g., laboratory values, physical examination findings, ECG changes) or identified from review of other documents, that are considered clinically significant will be documented on the AE page in the eCRF. Worsening of symptoms that are only detected on clinical effects rating scales will not be reported as AEs.

Adverse events will be assessed at each visit by direct questioning of the patient/parent/caregiver as well as elicited from physical examination by site staff. In addition, all sites in the study must ensure patients/parents/caregivers have a 24-hour telephone number to contact medical site staff for the duration of the study, in case of emergent AEs or SAEs.

If there is any doubt as to whether a clinical observation is an AE, the event should be reported.

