4.1.1 Screening

Screening evaluations must be completed within 6 weeks of signing the informed consent form (ICF) and these assessments can occur on multiple days, provided they are within the Screening Period. The Investigator will determine whether patients meet eligibility criteria and will collect the demographic and medical data permitting full characterization of the patient. Patients who screen fail may be rescreened once.

A record of patient screen failures will be maintained for patients who do not qualify for enrollment, including the reason for the failure. A baseline open muscle biopsy (from deltoid) will be performed at least 2 weeks prior to the Day 1 visit. This will allow full recovery from the surgery prior to obtaining baseline functional assessments. All attempts should be made to complete all screening assessments and confirm patient eligibility for the study prior to muscle biopsy collection to prevent biopsies from being performed on patients not eligible for the study. The time from signing the ICF to Day 1, including screening and open muscle biopsy collection cannot exceed 6 weeks.

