^l Refer to Section 6.2.2 for details regarding study drug administration. Prior to dosing, review of drug withholding criteria should be performed (See Section 6.2.4). For each dosing day, \pm 2 days of window may be allowed. However, administration of Study Drug needs to be separated by a minimum of 5 days between infusions

Table 3 Schedule of Pharmacokinetic Blood Sample Collection for the Japanese PK Cohort-Double-blind Period

| Week 1 | | | | | | | | Week 2 |
|----------|------------------|----------------------|------------------|-------------------|-------------------|--------------------|--------------------|----------|
| Day 1 | | | | | | | | Day 2 |
| Pre-dose | EOI | 15 minutes after EOI | 1 hour after EOI | 4 hours after EOI | 6 hours after EOI | 12 hours after EOI | 24 hours after EOI | Pre-dose |
| | within 5 minutes | ±5 minutes | ±15 minutes | | | | | |
| X | X | X | X | X | X | X | X | X |

Abbreviations: EOI = end of infusion; PK = pharmacokinetic

Table 4 Schedule of Sparse PK Blood Sample Collection for All Patients-Double-blind Period

| Week 1 | | Week 2 | Week 12 | Week 22 | | Week 46 | |
|----------|------------------|----------|-----------------------|-----------------------|------------------|-----------------------|------------------|
| Pre-dose | EOI | Pre-dose | Pre-dose ^a | Pre-dose ^a | EOI | Pre-dose ^a | EOI |
| | within 5 minutes | | | | within 5 minutes | | within 5 minutes |
| X | X | X | X | X | X | X | X |

Abbreviations: EOI = end of infusion; PK = pharmacokinetic.

^a On biopsy days, pre-dose PK samples should be collected before biopsy procedure.**Table 5 Schedule of Sparse PK Blood Sample Collection for All Patients-Open-label Period**

| Week 60 | Week 72 | Week 96 (or ET) |
|----------|----------|-----------------|
| Pre-dose | Pre-dose | Pre-dose |
| X | X | X |

Table 6 Immunogenicity Sample Collection-Double-blind Period

| Week 1 | Week 12 | Week 22 | Week 48 (or ET) |
|------------------|------------|------------|-----------------|
| Day 1 (Pre-dose) | (Pre-dose) | (Pre-dose) | (Pre-dose) |
| X | X | X | X |

Table 7 Immunogenicity Sample Collection-Open-label Period

| Week 60 | Week 72 | Week 96 (or ET) |
|----------|----------|-----------------|
| Pre-dose | Pre-dose | Pre-dose |
| X | X | X |

Table 8 ActiMyo Device Data Collection- Double-blind Treatment Period

| Beginning of Device Use ^a | End of Device Use ^a | Data Collection Duration |

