9.2.2 Relationship to Study Drug

The Investigator's assessment of an AE's relationship to study treatment is part of the documentation process, but it is not a factor in determining what is or is not reported in the study. All AEs, regardless of relationship, will be recorded in the eCRF. In addition, SAEs will be reported to regulatory authorities as required by local regulation ([Section 9.3.4](#)).

The relationship or association of the study drug in causing or contributing to the AE will be characterized using the classification and criteria presented in [Table 11](#).

Table 11 Guidelines for Determining the Relationship (if any) Between Adverse Event and the Study Drug

| AE Relationship | Definition |
|-------------------------|--|
| Definite | This relationship suggests that a definite causal relationship exists between treatment administration and the AE, and that other conditions (concurrent illness, progression/expression of disease state, or concurrent medication reaction) do not appear to explain the event. The event reappears or worsens if the study treatment is re-administered. |
| Probable | This relationship suggests that a reasonable temporal sequence of the event with treatment administration exists and, based upon the known pharmacological action of the treatment, known or previously reported adverse reactions to the treatment or class of treatment, or judgment based on the Investigator's clinical experience, the association of the event with the study treatment seems likely. The event disappears or decreases on cessation of study treatment. |
| Possible | This relationship suggests that the study treatment caused or contributed to the AE, i.e., the event follows a reasonable temporal sequence from the time of treatment administration or follows a known response pattern to the study treatment, but could also have been produced by other factors. |
| Unlikely Related | This relationship suggests an improbable (but not impossible) association between the study medication and the reported event. |
| Not Related | This relationship suggests no association between the study treatment and the reported event. |

Abbreviations: AE = adverse event.

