11.2.1 Analysis Populations

The primary efficacy analysis population will be the intent-to-treat (ITT) population, which consists of all randomized patients. All patients will be analyzed according to the treatment to which they are randomized.

The safety population will include all randomized patients who have received at least one dose of the study drug. All patients will be analyzed according to the treatment they have actually received.

The pharmacokinetic population will be a subset of the safety population and include subjects with evaluable pharmacokinetics data.

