11.3.4 Analysis of Safety Data

The summary of safety results will be presented by treatment group. All safety analyses will be performed on the safety population using the following common rules:

- The baseline value is defined generally as the last available value before randomization.
- Adverse event observation periods are defined as follows:
 - Pretreatment AEs are AEs that developed or worsened prior to the first dose of study drug

- On-treatment AEs are AEs that developed or worsened from the first dose of study drug to study completion/discontinuation. Summaries of TEAEs will include all on-treatment AEs.
- For quantitative safety parameters based on central laboratory/reading measurements descriptive statistics will be used to summarize results and change from baseline values by visit and treatment group.

11.3.4.1 *Adverse Events*

Treatment-emergent AEs, TEAEs assessed as related to study drug or to study procedures, and treatment-emergent SAEs will be summarized for each treatment group based on MedDRA coding of verbatim terms reported by Investigators.

Adverse event incidence tables will present, by system organ class (SOC) and preferred term, the number and percentage of patients experiencing an AE. Multiple occurrences of the same event will be counted once in the tables. The denominator for computation of percentages is the safety population within each treatment group.

Adverse event incidence tables will present, by SOC and preferred term, the number and percentage of patients experiencing an AE by severity and by relationship to treatment. In tabulating the severity of AEs, the highest severity will be assigned to a subject with more than one occurrence of the same AE. The highest level of association will be reported in subjects with differing relationships for the same AE.

Listings of all AEs, SAEs, deaths, and AEs leading to study discontinuation will be provided.

11.3.4.2 *Clinical Laboratory Evaluations*

Summary statistics of laboratory variables will be calculated for each visit or study assessment by treatment group. Shift tables showing the pattern of change from baseline to postbaseline visit(s) will be provided. Listings of laboratory data will be provided. For hematology and chemistry variables, the normal ranges will be provided, and abnormal laboratory values flagged and clinical significance indicated. A listing of clinically significant hematology and chemistry findings will be provided.

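### The protocol specifies no procedure-causality item for the promised summary of procedure-related TEAEs, and that summary's scope leaves out pre-dose complications of the baseline open biopsy

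*Combined protocol and SAP*

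**What the plan says.** **Causality.** Section 9.1 opens its list of AE data with "Information to be collected includes the as-reported event term" and gives, as the only causality entry, "Investigator-specified assessment of severity and relationship to study treatment". Section 9.2.2 introduces Table 11 with the statement that "The relationship or association of the study drug in causing or contributing to the AE will be characterized". All five grades of that table, from definite to not related, are graded against the study treatment. Section 9.3.4.1 asks the initial SAE report for causality with respect to the study drug.

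**Analysis.** Section 11.3.4.1 states: "TEAEs assessed as related to study drug or to study procedures, and treatment-emergent SAEs will be summarized for each treatment group". Section 11.3.4 runs all safety analyses on the safety population, which Section 11.2.1 defines thus: "The safety population will include all randomized patients who have received at least one dose of the study drug". It divides AEs into a pretreatment period, before the first dose, and an on-treatment period, which feeds the TEAE summaries. It assigns no table to the pretreatment period.

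**Biopsies.** Each boy has one open biopsy before treatment and one later. Section 4.1.1 says: "A baseline open muscle biopsy (from deltoid) will be performed at least 2 weeks prior to the Day 1 visit". Section 4.1.2 places the second at Week 12, 22 or 46. A footnote to Table 4 in Section 4.2 reads: "On biopsy days, pre-dose PK samples should be collected before biopsy procedure", so the second biopsy and a dosing visit can fall on the same day.

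**The concern.** The analysis section promises a result that the data-collection sections do not provide for. If the eCRF follows Sections 9.1 and 9.2.2 as written, each event receives a drug rating and no procedure rating. Someone would then have to decide after the fact, from event terms and dates, which events belong in the procedure-related summary.

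Scope is a second problem. The baseline biopsy precedes the first dose by rule, so its early complications are pretreatment AEs. A summary limited to TEAEs in dosed boys counts the burden of the second biopsy and largely passes over the first.

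At stake is a fair account of the harm done by study procedures. These are boys of 5 to 12 years who have two open muscle biopsies for a trial endpoint. The protocol itself treats bleeding as a matter to watch. It reports coagulation changes in animals (Section 1.3), excludes boys with raised aPTT, low platelets or drugs that raise bleeding risk (Section 5.2), checks platelets before every dose (Section 6.2.4.2), and gives a bleed after surgery as an example of an event that could be serious (Section 9). A report that follows the stated scope would undercount procedure-related complications.

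**Working it through.** The plan gives no biopsy total or complication count to reproduce. The check is a comparison of sections and one simple count.

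**Step 1: does any section ask for a procedure rating?**

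| Place | What it asks for | Procedure named? |
|---|---|---|
| Section 9.1, AE data list | Relationship to treatment | No |
| Section 9.2.2, Table 11 | Graded relationship to drug | No |
| Section 9.3.4.1, initial SAE report | Causality with respect to drug | No |
| Section 11.3.4.1, incidence tables | Breakdown by relationship to treatment | No |
| Section 11.3.4.1, TEAE summary | Related to drug or to procedures | Yes |

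Only the output names procedures. No section defines the rating, gives it a scale or tells the investigator to make it. The list in Section 9.1 is open-ended, and the one in Section 9.3.4.1 is a minimum. The finding is therefore that the protocol specifies no such item, not that none exists.

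**Step 2: which baseline-biopsy complications reach the summary?** Sections 9 and 11.3.4 count an event as treatment-emergent if it starts or worsens after the first dose.

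| Complication of the baseline biopsy | In the TEAE summary? |
|---|---|
| Starts before first dose, does not worsen | No |
| Starts before first dose, worsens afterwards | Yes |
| Starts after first dose | Yes |
| Any, in a boy never dosed | No (outside the safety population) |

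**Step 3: what share of open biopsies is the baseline biopsy?** Inputs: about 150 boys (Section 11.1); one baseline biopsy each (Section 4.1.1); at most one later biopsy each (Section 4.1.2); dropout of 10% (Section 11.1); discontinuation rates of 0.6% and 2.7% that Section 11.3.2.1 cites from previous studies. The later biopsies come from cohorts of 30, 40 and up to 80 (Sections 4.1.2 and 11.5.1), and 30 + 40 + 80 = 150 agrees with planned enrolment.

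Share = baseline / (baseline + post-baseline). With dropout d before the second biopsy, share = 150 / (150 + 150 × (1 − d)).

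- d = 0: 150/300 = 50.0%
- d = 0.6%: 150/(150 + 149.1) = 50.2%
- d = 2.7%: 150/(150 + 145.95) = 50.7%
- d = 10%: 150/(150 + 135) = 150/285 = 52.6%

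The number enrolled cancels, so an early stop to enrolment does not alter the share. Boys biopsied but never dosed would raise it. If 5 to 15 are assumed, with 10% dropout in the rest, the share is 155/290 = 53.4% to 165/300 = 55.0%. The documents give no figure for that group.

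This is a share of biopsies. The documents give no complication rate per biopsy, so it cannot be turned into a number of events.

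**The case against.** The strongest reply is that little is lost.

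- The eCRF and its completion guidelines are not shown, and Section 11.3.4.1 speaks of events assessed as procedure-related, which presupposes that someone makes the assessment.
- Section 11 defers some detail, such as interim thresholds, to a SAP. No separate table specification is in the combined document, so a pretreatment table could exist elsewhere.
- AEs are collected from consent (Section 9), SAEs are reported from consent whatever their cause (Section 9.3.4.1), all AEs are to be listed (Section 11.3.4.1), and screen failures are listed with reasons (Section 11.2).
- Keeping pre-dose events out of TEAE tables follows from the TEAE definition.
- The question whether the drug adds to surgical risk is answered by the blinded, randomized comparison after the second biopsy.

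Most of this stands, and it rules out four stronger readings that a reader might infer.

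1. That the procedure summary has no data behind it. The documents show only that the protocol does not specify the item.
2. That every baseline-biopsy complication is left out. Those that start or worsen after the first dose are TEAEs.
3. That an event on a biopsy day must be blamed on the drug or its cause is lost. Table 11 offers unlikely and not related, and the event term and onset date and time are recorded.
4. That baseline against on-treatment biopsy is the direct evidence on drug-added risk. It compares a first operation with a second one many weeks later. The randomized contrast of active with placebo is the direct evidence, and TEAEs are summarized by arm whatever their cause.

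Two things remain. No protocol section supports the procedure rating that Section 11.3.4.1 relies on. And a listing is not a summary: it gives no denominator, no specified procedure attribution, and no explicit assurance that boys never dosed are included, since Section 11.3.4 places all safety analyses on the safety population.

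**Conclusion.** The concern holds as a gap in attribution and tabulation, not in collection. The protocol promises a procedure-related summary without specifying its input. As scoped, that summary excludes baseline-biopsy complications that start before dosing and do not worsen, and all complications in boys biopsied but never dosed. The baseline biopsy accounts for 50.0% of open biopsies with no dropout and 52.6% with 10% dropout before the second one.

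This rests on one baseline and at most one later biopsy per boy, and on reading Sections 9 and 11.3.4 as written. If the eCRF already records relationship to procedure, the first part reduces to saying so in the protocol; the second part is unchanged. The number of boys never dosed should be small, because Table 1 places the baseline biopsy after eligibility is confirmed, but the documents do not state it.

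No efficacy endpoint or error rate is affected, and drug safety is still judged by the randomized comparison of all TEAEs. It is an inexpensive improvement that should be made, because the stated scope would undercount the harm of open surgery in children.

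**What to change.** - **Sections 9.1, 9.2.2 and the SAE form (Section 9.3.4.1):** add an item for relationship to study procedure (biopsy, infusion procedure, other) beside the drug-relationship item. If the eCRF already has it, state that in the protocol.
- **Section 11.3.4.1:** summarize procedure-related AEs from consent onward in all boys who had a biopsy. Split the table into (a) baseline biopsy, with all boys biopsied as denominator, including those never dosed, and (b) post-baseline biopsy, by arm, with boys who had that biopsy as denominator. The TEAE tables stay as they are.

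The cost is one eCRF field and one extra table. AEs are already collected from consent, so no visit, procedure or sample is added.
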